8.1 PHYSICAL EXAMINATION

8.1.1 FULL PHYSICAL EXAM

The Principal Investigator or qualified designee will perform a complete physical exam during the Screening period. Clinically significant abnormal findings should be recorded as medical history. The time points for physical exams are described in Table 3.0. After the first dose of trial treatment, new clinically significant abnormal findings should be recorded as AEs.

8.1.2 DIRECTED PHYSICAL EXAM

The Principal Investigator or qualified designee will perform a directed physical exam as clinically indicated prior to the administration of the trial treatment. New clinically significant abnormal findings should be recorded as AEs.

8.1.3 VITAL SIGNS

Vital signs include temperature, pulse, respiratory rate, weight and blood pressure. The Principal Investigator or qualified designee will take vital signs at screening, prior to the administration of each dose of trial treatment and during the follow-up period as specified in the Trial Flow Chart (Section 8.0). Height will be measured at Screening.

8.1.4 RESPONSE ASSESSMENT

MRI of the brain will be the primary radiological method of disease assessment using modified RECIST 1.1. Treatment decisions will be made according to modified RECIST 1.1 while other measurement criteria will be utilized as secondary endpoints including iRANO criteria (See Appendix 1). Quantitative imaging changes on multiparametric MRI will be captured to determine early biomarkers of immune response. Standard of care brain MRI with intravenous gadolinium contrast and contrast enhanced CT chest/abdomen/pelvis or PET-CT, as clinically indicated, will be used to assess both intracranial and extracranial disease at Screening and every 4 weeks for the first 12 weeks, then every 8 weeks for the first year, then every 12 weeks until progression or discontinuation of study treatment, whichever comes

later. Imaging window is \pm 7 days. If scans performed within 4 weeks of discontinuation, repeat scans are not required. Screening MRI and CT assessments must occur within 28 days prior to day 1.

If an MRI, CT chest/abdomen/pelvis or PET-CT is not already performed as standard of care per Schedule of Assessments in Section 8.0, the principal investigator may choose to perform either or both procedures for assessing the progress of the patient.

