Objectives	
Phase I Primary Objective
 
Establish safety profile and recommended phase II dose for combining Bintrafusp Alfa (M7824) and pimasertib in patients with brain metastases. 
Phase II Primary Objective
 
Time to intracranial progression (defined as progression of existing lesions and development of new lesions by modified RECIST 1.1) and Overall survival. 
Secondary Objectives
 
Intracranial progression 4, 8, 12, 16 weeks and every 8 weeks thereafter.Intracranial objective response rate as measured by RANO-BM, iRANO, and RECIST 1.1.Time to second intracranial progression after Salvage SRSOverall survival rate at 24, 52, 68 weeks.Frequency of grade 3+ intracranial toxicities at 4, 12, 24, 36, 52, and 68 weeks..Frequency of extracranial progression and response rate at 8, 16, 24, and every 8 weeks thereafter.Frequency of neurocognitive decline at 24, 52, and 68 weeks (optional).Changes in neurocognitive function and health-related quality of life.Dose, duration and frequency of steroid use for symptomatic management. 
Exploratory Objectives
 
Identify molecular and/or immunological markers from biospecimens (tissue, blood, and CSF) that are associated with treatment response and toxicity.Identify imaging biomarkers of response and toxicity (acute radiation effect/radionecrosis and neurocognitive changes) from multiparametric MRI and/or delayed PET that predict treatment response and toxicity.Dose, duration and frequency of steroid use for symptomatic management.To evaluate the potential correlation between mutational burden and tumor response

Proprietary Information of MD Anderson

Study Design

- Identify correlative or surrogate relationship between systemic (blood) and imaging markers and treatment outcomes.

This study is an open-label Phase I/II trial to determine the safety and efficacy of pimasertib in combination with Bintrafusp Alfa (M7824) in patients with brain metastases. The Phase I study will accrue patients with melanoma, lung, and breast cancers to a dose escalation phase as described below. The Phase II study will include expansion cohorts, of 10 patients each with melanoma, lung, breast brain metastases, to better characterize the safety profile and efficacy of the combination and its impact on time to intracranial progression.

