- e Prothrombin time/International Normalized Ratio, Activated Partial thromboplastin time.
- f MRI Scan will be performed every 4 weeks for the first 16 weeks, then every 8 weeks until progression or discontinuation of study treatment, whichever comes later. Imaging window is \pm 7 days. If scans performed within 4 weeks of discontinuation, repeat scans are not required.
CT-CAP or PET-CT will be performed every 8 weeks until progression or discontinuation of study treatment, whichever comes later. Imaging window is \pm 7 days. If scans performed within 4 weeks of discontinuation, repeat scans are not required.
Please note that if an MRI, CT chest/abdomen/pelvis or PET-CT is not already performed as standard of care per Schedule of Assessments in Section 8.1.4, the investigator may choose to perform either or both procedures for assessing progress of the patient.
- g Obtain archival only if tissue is post PD-1 exposure for melanoma and lung cancer patients. See Section 8.7.1 for additional details.
- h Patients with biopsiable extracranial disease may have tissue collected. See Section 8.8.
- i Cerebrospinal Fluid may be obtained if testing for LMD. See section 8.7.3 for additional details.
- j See Section 8.7.
- k CBC & CMP is done every 2 weeks (+/- 7 days) prior to infusion.
- l Patients will have ophthalmological evaluation at baseline and every 12 weeks. See section 8.3.
while receiving protocol therapy
- m Serum chemistry includes the tests listed (glucose, BUN, creatinine, sodium, potassium, magnesium, chloride, bicarbconate, calcium, phosphorus, total and direct bilirubin, ALT, AST, ALP, LDH, total protein, albumin, CPK, and uric acid). CMP is done every 2 weeks prior to infusion.
- n Height only taken at Screening
- o There will also be a Neurocognitive exam at the 3-month mark
- p A follow up call will be done at 90 days to assess patient safety.

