8.8 TUMOR IMAGING AND ASSESSMENT OF DISEASE

All subjects will undergo CT scanning and MRI of the brain at the time points specified in the Schedule of Events. CT and MRI scans will be assessed locally per the modified RECIST 1.1, RANO-BM, and iRANO criteria. Up to 5 systemic and 5 brain lesions will be followed for efficacy per the criteria. Patients with biopsiable extracranial disease may have tissue collected.

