9.3.2 INTRACRANIAL PROGRESSION FREE SURVIVAL

The time to intracranial progression, determined by modified RECIST 1.1, will be calculated from the time of study enrollment to intracranial progression (event) or the last follow-up date if the patient has not developed the intracranial progression yet (censored). The median time to intracranial progression and intracranial progression free survival rates at specific times will be estimated and reported with 95% confidence interval utilizing the method of Kaplan and Meier. This will serve as the primary analysis and will be performed overall and within each treatment group. Completing risk analysis may be considered by treating events outside of intracranial disease progression (e.g. events such as extracranial disease progression, early dropout due to toxicity, or death) as competing risks.

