The RECIST criteria should be used to assess response to treatment. Only patients with measurable disease should be entered in the study. Measurable extracranial disease is defined as the presence of one lesion that can be accurately measured in at least one dimension (longest diameter to be recorded) as ≥ 2.0 cm with conventional techniques (or as ≥ 1.0 cm by spiral CT). Evaluable lesions should be followed for the assessment of response. Non-measurable lesions include bone lesions, ascites, pleural/pericardial effusion, lymphangitic carcinomatosis, abdominal masses that are not confirmed by CT, and cystic lesions. Disease progression and response evaluations for intracranial and extracranial disease will be determined according to the definitions established in the Response Evaluation Criteria in Solid Tumours (RECIST v1.1). Minor modifications will be applied to the assessment of intracranial lesions:

- General: target lesions should be representative of the subject's baseline tumor burden and should be selected based on their size (i.e. lesions with the longest diameter) and their suitability for accurate repeat assessment.
- Intracranial lesions: (the modifications to RECIST v1.1. impact the number and the minimal size of the target lesions selected at baseline) up to five lesions should be selected as target lesions; all brain lesions in excess of these five target lesions have to be regarded as non-target lesions. Measurable lesions are defined as those that can be accurately measured in at least one dimension with the longest diameter ≥ 5 mm when evaluated with contrast-enhanced MRI. Contrast-enhanced MRI is the only imaging modality accepted for assessment of intracranial lesions.
- Extracranial lesions: up to two lesions per organ representative of all involved organs should be selected as target lesions; the total number of target lesions should not exceed five and all lesions in excess of these five target lesions have to be regarded as non-target lesions.

Baseline Documentation of Intracranial Target and Non-Target Lesions

- All baseline lesion assessments must be performed within 28 days of the first dose of study treatment.

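### The protocol contradicts itself on whether the brain MRI that dates intracranial progression is required or left to the investigator when routine care does not supply it

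*Combined protocol and SAP*

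**What the plan says.** The phase II primary objective in the Trial Summary is "Time to intracranial progression (defined as progression of existing lesions and development of new lesions by modified RECIST 1.1) and Overall survival". The RECIST v1.1 appendix states that "Contrast-enhanced MRI is the only imaging modality accepted for assessment of intracranial lesions". Intracranial progression at weeks 4, 8, 12 and 16 is a secondary objective (section 4.2).

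Two places make the imaging compulsory:
- Section 8.8: "All subjects will undergo CT scanning and MRI of the brain at the time points specified in the Schedule of Events".
- Table 3 footnote f, opening line: "MRI Scan will be performed every 4 weeks for the first 16 weeks", followed by 8-weekly scans.

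Two places make a scheduled scan discretionary when routine care has not supplied it:
- Section 8.1.4, second paragraph: "the principal investigator may choose to perform either or both procedures for assessing the progress of the patient".
- Table 3 footnote f, closing lines: "the investigator may choose to perform either or both procedures for assessing progress of the patient".

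Section 8.1.4 also calls the brain MRI standard of care and includes a qualifier about clinical indication. That qualifier follows the CT and PET-CT wording, and it is unclear whether it reaches the MRI. The same section gives fixed intervals and a window of ±7 days.

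Under section 9.3.2 the clock starts at enrollment and stops at progression on the modified RECIST criteria. For patients without that event, the section sets the end of observation as follows: "or the last follow-up date if the patient has not developed the intracranial progression yet (censored"). It gives no rule for a missed scan.

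**The concern.** Radiographic intracranial progression is seen only on these MRIs. If the protocol both requires a scheduled MRI and lets the investigator decide whether to do it, two things follow. Staff cannot tell whether an omitted scan is a deviation. The analyst cannot assume that patients were assessed on a common calendar.

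Phase II is meant to estimate time to intracranial progression for use in larger studies. Omitted scans push recorded dates later, and censoring at last follow-up does not correct for this. A patient who attends clinic without an MRI counts as progression-free up to that visit. The early time points in section 4.2 are the most exposed, because they rely on 4-weekly scans that routine care may not provide.

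**Working it through.** **1. Can the passages be reconciled as written?** Section 8.8 requires scans at the times in the schedule. The schedule is Table 3, and its footnote f contains the discretionary sentence, so section 8.8 does not override it. For the schedule, the discretionary sentence in footnote f points to section 8.1.4, and the one in section 8.1.4 points back to section 8.0. Neither settles the matter.

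**2. Does the milder reading remove the problem?** The sentence may only have been meant to let the study obtain a scan that routine care does not supply. A permission is still not a duty, and doing neither scan would be consistent with it. Elsewhere the protocol uses must for obligations (screening scans in 8.1.4, eye examinations in 8.3) and may for optional items (biopsies in 8.2.2).

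**3. Is there a plan figure to reproduce?** No. Phase II has no effect size, power or event target. The figures below show scale only.

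**4. Illustration: routine care supplies 8-weekly MRI only.** These assumptions are not in the documents: exponential time to progression with true median m weeks, no deaths, and detection at the first scan on or after progression. Write S(t) = 2^(−t/m). The true mean time is m/ln 2. Mean recorded time is the sum, over scan intervals, of interval length times S at the start of the interval.

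- Footnote f calendar: 4[1 + S(4) + S(8) + S(12)] + 8·S(16)/[1 − S(8)].
- 8-weekly calendar: 8/[1 − S(8)].
- The difference simplifies to 4[1 − S(4)][1 + S(8)].

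At m = 12: S(4) = 0.794, S(8) = 0.630, S(12) = 0.500, S(16) = 0.397, and the true mean is 17.31 weeks.
- Footnote f: 11.69 + 8.58 = 20.27, a mean delay of 2.96 weeks.
- 8-weekly: 8/0.370 = 21.62, a mean delay of 4.31 weeks.
- Added delay: 4 × 0.206 × 1.630 = 1.35 weeks.

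| True median (weeks) | Added mean delay (weeks) | True progression by week 4 | Recorded by week 4 with 8-weekly MRI |
|---|---|---|---|
| 6 | 2.07 | 37% | 0% |
| 12 | 1.35 | 21% | 0% |
| 24 | 0.78 | 11% | 0% |

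With 8-weekly scans the week-12 value repeats week 8 (at m = 12, 37% against a true 50%). Weeks 8 and 16 are recovered exactly (37% and 60%).

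**5. Illustration: scans skipped at random on the footnote f calendar, m = 12.**

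| Scans skipped | Mean delay (weeks) |
|---|---|
| 0% | 2.96 |
| 10% | 3.64 |
| 25% | 5.02 |
| 50% | 9.49 |

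The loss is small if omissions are rare and material if they are common. The documents do not say which to expect.

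**The case against.** The strongest reply is that the protocol does mandate imaging. Section 8.8 covers all subjects, footnote f opens with a firm schedule, section 8.1.4 gives intervals and a window, and the Table 3 grid marks MRI at every cycle from 2 to 8. Section 3.0 presents early imaging as a deliberate part of the design. On that view the discretionary sentence is loose wording about who arranges the scan.

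Much of this stands. A reader might infer that endpoint imaging is simply left to standard of care, so that progression is dated by who happens to be scanned. The documents do not support that: the mandatory statements are explicit, and the fault is a contradiction. It remains a fault because the discretion appears twice, once inside the schedule that section 8.8 relies on.

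Three further inferences should be resisted.
- **Scanning that follows clinical worry.** This is plausible in an open-label trial, but the documents do not show it and the figures above do not model it.
- **A recorded median of 16 weeks instead of 12.** This comes from placing the assumed median exactly on the week-12 scan. At a true median of 13 weeks both calendars record 16.
- **All the early progression rates being lost.** In the 8-weekly example only weeks 4 and 12 are lost.

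It is also fair to say that phase II tests no efficacy hypothesis, overall survival does not depend on MRI, and there is no comparison arm to bias. The RECIST appendix also lets clinical decline with evidence of progression count as progressive disease, so not every event needs a scan.

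**Conclusion.** The point holds as an internal inconsistency affecting one of the two phase II primary endpoints. The protocol both requires the scheduled brain MRI and makes it discretionary when routine care does not provide it, and nothing else in the document decides between them. Any omission moves the radiographic progression date later, never earlier, and the censoring rule in 9.3.2 credits unscanned follow-up as progression-free.

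Its size is not known. Under exponential progression, no deaths and 8-weekly routine scanning, the cost is about 0.8 to 2.1 weeks of added mean delay over true medians of 24 down to 6 weeks, plus loss of the week-4 and week-12 radiographic estimates. Because the trial is estimation-only, this should be corrected but is not a must-fix defect.

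**What to change.** Reconcile section 8.1.4, Table 3 footnote f and section 8.8:
- Replace the discretionary sentence in both places with a statement that any scheduled brain MRI not done as standard of care is done as a study procedure within the ±7-day window. Apply the same rule to scheduled CT or PET-CT for the extracranial endpoints.
- State in 8.1.4 that the standard-of-care and clinical-indication wording does not make the brain MRI optional.
- Name one governing imaging calendar. Section 8.1.4 has 4-weekly scans to week 12, footnote f has them to week 16, and the Table 3 grid marks MRI at every cycle through cycle 8.
- Record each missed scheduled scan as a protocol deviation.

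A useful companion change in 9.3.2 is to censor patients without progression at the last evaluable MRI and to say how missed scans are handled.

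The cost is a few sentences in an amendment. No scan is added beyond the calendar chosen, but the study must cover scheduled scans that routine care does not supply. The documents do not show how many that would be.

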8.2 BIOPSY AND ARCHIVAL TUMOR TISSUE SAMPLE

8.2.1 ARCHIVAL TUMOR TISSUE SAMPLE

Archival tumor tissue samples obtained outside of this study for other purposes will be collected, if available, from all patients. All samples must be representative formalin-fixed paraffin-embedded (FFPE) tumor specimens in paraffin blocks (preferred) or at least 10 unstained slides, with an associated pathology report, for correlative evaluation. Archival tissue for melanoma and lung cancer patients must be after PD1 exposure.

8.2.2 BIOPSY

Patients with biopsiable extracranial disease may have tissue collected pretreatment and at Cycle 2 (4 weeks after the start of treatment). An additional optional biopsy may be collected at Cycle 5, if accessible, but is not required. All biopsies are optional for enrollment, but highly encouraged for pretreatment and Cycle 2. If standard of care biopsies are required, additional, optional tissue may be acquired as part of this protocol. Acceptable samples include core-needle biopsies for deep tumor tissue (minimum of three cores) or excisional, incisional, or punch biopsies for cutaneous, subcutaneous, or mucosal lesions.

For core-needle biopsy specimens, at least three cores should be submitted for evaluation. Cores will be distributed to FFPE and snap frozen equally.

8.3 OPHTHALMOLOGY

OPHTHALMOLOGIC EXAMINATION MUST BE PERFORMED AT THE BASELINE, EVERY 12 WEEKS OF TREATMENT AND AT END OF TREATMENT.

The objective of baseline ophthalmologic examination is to evaluate for evidence of retinal pathology that may be a risk factor for central serous retinopathy or RVO. Ophthalmologic examination must be performed by a qualified ophthalmologist. Riskfactors for RVO include uncontrolled serum cholesterol, hypertriglyceridemia, hyperglycemia, hypertension, and glaucoma.

Baseline and serial surveillance ophthalmologic examination will include visual acuity testing, intraocular pressure measurements by tonometry, slit lamp ophthalmoscopy, indirect ophthalmoscopy, and Spectral-domain optical coherence tomography, if not available, may be substituted with time- domain optical coherence tomography.

8.4 LABORATORY ASSESSMENTS

All labs will be processed locally at MDACC.

8.5 ELECTROCARDIOGRAM

A standard 12-lead ECG will be performed using local standard procedures at Screening. Clinically significant abnormal findings should be recorded as medical history.

Clinically significant abnormal findings seen on the follow-up ECGs should be recorded as adverse events.

8.5.1 ECHO/MUGA

An ECHO/MUGA will be done at baseline and every 2 months. Please refer to Table 3.0 for additional information. Clinically significant abnormal findings seen on the follow-up ECHOs should be recorded as adverse events.

8.6 NEUROLOGICAL FUNCTION TESTING

Neurologic functioning will be evaluated using NANO. This objective and quantifiable assessment will evaluate nine major domains for subjects with brain tumors. The domains include: gait, strength, ataxia, sensation, visual field, facial strength, language, level of consciousness, behavior and overall. Each domain is rated on a scale of 0 to 3 where 0 represents normal and 3 represents the worst severity. A given domain should be scored non-evaluable if it cannot be accurately assessed due to preexisting conditions, co-morbid events and/or concurrent medications. The evaluation is based on direct observation/testing performed during routine office visits. The NANO scale will be completed by the principal investigator or designated study physician prior to dosing Day 1 Week 1 (baseline) and then at the time points indicated in on the schedule of events.

Neuropsychological testing will be performed with a standardized battery routinely used to assess patients with brain metastases at MDACC, including in the previously published Chang et al. trial [55]. This evaluation will be performed by a trained psychometrist under the supervision of [name], a licensed, board certified clinical neuropsychologist in the Department of Neuro-Oncology. The following tests were selected because they are widely used, standardized psychometric instruments that have been shown to be sensitive to changes in neurologic disease as well as treatment effects of cancer treatment in other clinical trials. Normative data have been published for all tests that take into account age, education, sex and handedness, where appropriate. These tests were also selected to minimize practice effects associated with repeated administration. The memory test has six alternate forms and the verbal fluency test has two alternate forms. The other tests measure motor and information processing speed and are relatively resistant to the effects of practice.

The total time for neuropsychological testing, including the quality of life (QOL) and symptom measures, is about 45 minutes.

Domain	Test	Administration Time (minutes)
Memory	Hopkins Verbal Learning Test-Revised (HVLT-R)	5
	WAIS-IV Digit Span	
Attention Span	Trail Making Test, Part A	3
Processing Speed	WAIS-IV Coding	3

Executive Function	Trail Making Test, Part B	5
	Controlled Oral Word Association (COWA)	5
Verbal fluency		5
Motor Dexterity	Lafayette Grooved Pegboard	5
PRO	MD Anderson Symptom Inventory – Brain Tumor	10

ECOG Evaluation

Eastern Cooperative Oncology Group (ECOG) Evaluation will be performed at Screening and at each cycle for every patient. The principal investigator or qualified designee will assess ECOG status (see Appendix 4) at screening, additional time points for assessment of ECOG must be performed.

